5.3 Blinding

This is an open-label trial. There will be no randomization or blinding.

5.4 Drug Logistics and Accountability

All study drugs will be stored at the investigational site in accordance with good clinical practice (GCP) and GMP requirements and will be inaccessible to unauthorized personnel. Special storage conditions and a complete record of batch numbers and expiration dates can be found in [name] study file; the site-relevant elements, of this information will be available in the ISF. The responsible site personnel will confirm receipt of study drugs and will use the study drugs only within the framework of this clinical study and in accordance with this protocol. Receipt, distribution, return and destruction (if any) of the study drugs must be properly documented according to Moffitt Cancer Center protocol.

6. Visit schedule and Assessments

6.1 Screening First Visit

Screening examinations will only be performed after having received the subject's written informed consent.

The following examinations will be performed within 28 days prior to the first treatment:

- Written subject informed consent to be obtained prior to any screening assessments.
- Complete medical history and physical examination, including demographics, surgery, therapies, medications, smoking, alcohol history, co-existing diseases, allergies, NYHA classification, vital signs (heart rate, respiration rate, temperature, and BP), weight and review of systems.
- Baseline toxicities / AEs
- ECOG Performance Status Assessment
- 12-lead ECG
- Radiologic assessment: CT scan or MRI with tumor measurement and disease assessment of non-measurable disease
- Coagulation (PT-INR and aPTT)
- Hematology (hemoglobin, HCT, RBC, WBC count with differential (neutrophils, bands, lymphocytes, monocytes, eosinophils and basophils) and platelet count
- Chemistry (ALT, AST, alkaline phosphatase, total bilirubin, direct bilirubin, lactate dehydrogenase (LDH), creatine kinase, lipase, amylase, glucose, calcium phosphate, magnesium, bicarbonate, sodium, potassium, chloride, creatinine, blood urea nitrogen (BUN), total protein and albumin
- Urinalysis
- Hepatitis and HIV test
- Serum pregnancy test (if applicable)
- Radiologic assessment tests (CT scan or MRI) performed up to 4 weeks prior to

obtaining informed consent can be used for screening purposes.

6.2 Cycle 1 Day 1

- History and assessment to include physical examination, vital signs (heart rate, respiration rate, temperature and BP) and review of systems
- Toxicity/AE assessment
- ECOG Performance Status Assessment
- Hematology (hemoglobin, HCT, RBC, WBC with differential (neutrophils, bands, lymphocytes, monocytes, eosinophils and basophils) and platelet count
- Chemistry (ALT, AST, AP, total bilirubin, direct bilirubin, glucose, calcium, phosphate, magnesium, bicarbonate, sodium, potassium, chloride, creatinine, BUN, total protein and albumin
- Screening hematology, platelet count and chemistry can be used for cycle 1 day 1 if screening tests are done within 5 days of cycle 1 day 1.
- Issue a new diary card (Appendix B)
- Urinalysis

6.3 Cycle 1 Day 15

- Hematology (hemoglobin, HCT, RBC, WBC with differential (neutrophils, bands, lymphocytes, monocytes, eosinophils and basophils) and platelet count
- Chemistry (ALT, AST, AP, total bilirubin, direct bilirubin, calcium, phosphate, magnesium, bicarbonate, sodium, potassium, chloride, creatinine, BUN, total protein and albumin

6.4 Subsequent cycles (Cycle X Day 1)

- History and assessment to include brief examination, vital signs (heart rate, respiration rate, temperature and BP) and review of systems
- Toxicity/AE assessment
- ECOG Performance Status Assessment
- Hematology (hemoglobin, HCT, RBC, WBC with differential (neutrophils, bands, lymphocytes, monocytes, eosinophils and basophils) and platelet count
- Chemistry (ALT, AST, AP, total bilirubin, direct bilirubin, glucose, calcium, phosphate, magnesium, bicarbonate, sodium, potassium, chloride, creatinine, BUN, total protein and albumin
- UA (if dipstick or routine urinalysis indicates proteinuria $\geq 2+$, a 24-hour urine collection must be obtained in 2 weeks before next dose of ramucirumab)
- Return an old diary card and issue a new diary card

6.5 Subsequent cycles (Cycle X Day 15)

- Hematology (hemoglobin, HCT, RBC, WBC with differential (neutrophils,

- bands, lymphocytes, monocytes, eosinophils and basophils) and platelet count
- Chemistry (ALT, AST, AP, total bilirubin, direct bilirubin, calcium, phosphate, magnesium, bicarbonate, sodium, potassium, chloride, creatinine, BUN, total protein and albumin

6.6 After every 3rd cycle (Cycle 3 Day 1, Cycle 6 Day 1, etc.)

- Tumor measurement/disease assessment according to RECIST 1.1 (please see Appendix B)
- History and assessment to include brief examination, vital signs (heart rate, respiration rate, temperature and BP) and review of systems
- Toxicity/AE assessment
- ECOG Performance Status Assessment
- Hematology (hemoglobin, HCT, RBC, WBC with differential (neutrophils, bands, lymphocytes, monocytes, eosinophils and basophils) and platelet count
- Chemistry (ALT, AST, AP, total bilirubin, direct bilirubin, glucose, calcium, phosphate, magnesium, bicarbonate, sodium, potassium, chloride, creatinine, BUN, total protein and albumin
- UA (if dipstick or routine urinalysis indicates proteinuria $\geq 2+$, a 24-hour urine collection must be obtained in 2 weeks before next dose of ramucirumab)
- Return an old diary card and issue a new diary card

6.7 End of Treatment Visit and Follow up

End of Treatment Visit

- History and assessment to include brief examination, vital signs (heart rate, respiration rate, temperature and BP) and review of systems
- Toxicity/AE assessment
- ECOG Performance Status Assessment
- Hematology (hemoglobin, HCT, RBC, WBC with differential (neutrophils, bands, lymphocytes, monocytes, eosinophils and basophils) and platelet count
- Chemistry (ALT, AST, AP, total bilirubin, direct bilirubin, LDH, glucose, calcium, phosphate, magnesium, bicarbonate, sodium)
- UA
- Tumor measurement/disease assessment according to RECIST 1.1 (please see Appendix B) may be conducted if it has not been performed within the last 4 weeks.

Safety Follow-Up Visit

The mandatory Safety Follow-Up Visit should be conducted approximately 30 days after the last dose of trial treatment. All AEs that occur prior to the Safety Follow-Up Visit should be recorded. Subjects with an AE of Grade > 1 will be followed until the resolution of the AE to Grade 0-1 or until the beginning of a new anti-neoplastic therapy, whichever occurs first. SAEs that occur within 90 days of the end of treatment or before initiation of a new anti-cancer

treatment should also be followed and recorded.

Survival Follow-up

Once a subject experiences confirmed disease progression or starts a new anti-cancer therapy, the subject moves into the survival follow-up phase for 6 months and should be contacted by telephone every 12 weeks to assess for survival status until death, withdrawal of consent, or the end of the study, whichever occurs first.

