- k. Can be performed over the phone. After off treatment following disease progression, physical assessments (with lab tests performed at the discretion of the treating investigator) should take place every 3 months for up to two years or death.
- l. A diary card will be issued on day 1 of each cycle and the issued diary card will be returned on subsequent cycle
- m. Radiologic tests (CT scan or MRI) performed up to 4 weeks prior to obtaining informed consent can be used for screening purposes.

- n. Restaging imaging only to be performed if not done within the last 4 weeks

7. Assessment types

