9.3 Statistical analysis

Overall survival (OS) is defined as the time from starting on trial to date of death due to any cause and progression-free survival (PFS) is defined as the duration of time from start of treatment to time of progression or death, whichever comes first. The final analysis will be conducted after the follow-time of the last patient exceeds 6 months. The primary endpoint of the study is OS at 6 month. The experimental treatment will be deemed to have good activity if ≥ 15 out of 25 evaluable patients survive 6 months or more. OS will be estimated using the Kaplan-Meier method and the two-sided 95% confidence interval (CI) for median OS will be computed using log-log transformation.

The secondary endpoints in this study include toxicity, PFS and the objective response rate (ORR) defined as (complete response (CR) + partial response (PR)) using RECIST 1.1 criteria (Appendix A). ORR will be reported with 95% CI computed by the Clopper-Pearson method. The frequency and severity of adverse events and tolerability of the regimen will be summarized using descriptive statistics. PFS with 95% CI will be estimated. As exploratory objective, the association between biomarkers and clinical outcomes (ORR, OS and PFS) will be examined using multiple logistic regression and the multivariable Cox regression model. A p-value of <0.05 will be considered statistically significant. Frequency and severity of adverse events will be summarized using descriptive statistics.

10. Data Recording

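### Survival follow-up is six months after progression in Section 6.7 but up to two years in the calendar; applied literally, the six-month limit makes OS censoring depend on progression and can bias median OS

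*Combined protocol and SAP*

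**What the plan says.** Three places bear on how long survival is followed.

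- **Section 6.7, Survival Follow-up.** After confirmed progression or the start of new anti-cancer therapy, "the subject moves into the survival follow-up phase for 6 months and should be contacted by telephone every 12 weeks". The sentence goes on: "to assess for survival status until death, withdrawal of consent, or the end of the study, whichever occurs first".
- **Section 6.8, calendar footnote k.** This is the only footnote on the survival follow-up row. It allows contact by phone and then says: "After off treatment following disease progression, physical assessments" "should take place every 3 months for up to two years or death".
- **Section 9.3.** OS is the "time from starting on trial to date of death due to any cause". "OS will be estimated using the Kaplan-Meier method", and the "two-sided 95% confidence interval (CI) for median OS will be computed using log-log transformation". On timing: "The final analysis will be conducted after the follow-time of the last patient exceeds 6 months".

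Neither Section 9.2 nor Section 9.3 says when a living patient is censored for OS or which follow-up length applies. Section 4.3 expects those who discontinue to comply with survival procedures. Yet Section 6.7 starts survival follow-up only at progression or new therapy, and footnote k only after progression.

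**The concern.** Site staff could stop calling six months after progression and be compliant with one half of the Section 6.7 sentence, while other staff follow the other half or footnote k. On the six-month reading, the date on which a living patient leaves the risk set is the progression date plus six months. Progression predicts death, so this is not the independent censoring that Kaplan-Meier and Cox models assume. After month 6, patients who progressed long ago drop out of the risk set. Those left to represent them have not progressed, or progressed recently.

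At stake are median OS (the only OS quantity for which the plan states a confidence interval), the later part of the curve, and the exploratory biomarker models for OS. Median OS is also the figure most likely to be set beside the published medians in the protocol's introduction.

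**Working it through.** **1. The plan's own figure.** The documents give no figure for OS bias. Their one checkable figure is the two-stage rule of Section 9.2 (continue at 7 or more of 15, success at 15 or more of 25):

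P(success) = Σ over x = 7 to 15 of Bin(x; 15, p) × P(Bin(10, p) ≥ 15 − x).

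This gives 0.0951 at p = 0.45 and 0.9004 at p = 0.70, matching the stated 10% and 90%.

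**2. Is the primary endpoint touched?** Progression comes after the start on trial, so progression + 6 months comes after month 6. The 6-month estimate and both counts are unchanged. (Two calls 12 weeks apart reach day 168, against about day 183 for six months. Only a patient who progressed in roughly the first two weeks could be last known alive just short of month 6.) For the same reason, a median at or below 6 months is not moved.

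**3. Size in a simple model.** Inputs from the documents are median PFS/OS of 2.9/8.7 months for TAS 102 (Section 1.4) and 4.4/9.6 months for ramucirumab plus paclitaxel (Section 1.3). Assumptions, not in the documents: exponential times, every patient progresses before death, and no other censoring. Independent administrative censoring would cost precision but would not change the large-sample bias.

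Let a = ln 2 / median PFS and b = ln 2 / median post-progression survival.

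- True curve: S(t) = (b·e^(−at) − a·e^(−bt)) / (b − a).
- After month 6, the ratio of progressed to progression-free patients still at risk is constant: r = a(1 − e^(−6(b−a))) / (b − a).
- The hazard that Kaplan-Meier sees is h = b·r / (1 + r).
- The median it reads is 6 + ln(2·S(6)) / h.
- The share censored by the rule is 0.5^(6 / median post-progression survival).

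For 2.9/8.7, a post-progression median of 4.35 months gives S(8.7) = 0.50. Then a = 0.2390, b = 0.1593, S(6) = 0.6765, r = 1.839 and h = 0.1032. The median read is 6 + ln(1.353)/0.1032 = 8.9. For 4.4/9.6, a post-progression median of 3.55 months gives S(6) = 0.7173, r = 0.846 and h = 0.0895, so 6 + ln(1.4346)/0.0895 = 10.0.

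| Median PFS | Post-progression median | True median OS | Read as | Share censored |
|---|---|---|---|---|
| 2.9 | 4.35 (matches 8.7) | 8.7 | 8.9 | 38% |
| 4.4 | 3.55 (matches 9.6) | 9.6 | 10.0 | 31% |
| 2.9 | 6 | 10.5 | 11.1 | 50% |
| 2.9 | 8 | 12.6 | 13.7 | 59% |
| 4.4 | 6 | 12.5 | 14.0 | 50% |
| 4.4 | 8 | 14.7 | 17.2 | 59% |

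The lower four rows assume post-progression survival longer than either benchmark pair implies. Simulation of 400,000 patients agrees with those four rows.

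**4. Sensitivity to the assumptions (simulation).**

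- *Some first events are deaths.* At a post-progression median of 6 months, with 20% of first events being deaths, the bias falls from +5.7% to +1.5% at PFS 2.9 and from about +11% to +5% at PFS 4.4.
- *Early progressors also die faster after progression* (gamma frailty, 10% of first events deaths). The bias grows. With variance 0.3, 9.1 reads 9.5 and 12.9 reads 15.2. With variance 0.6, 14.3 reads 18.6.
- *Post-progression hazard falls with time* (Weibull). With shape 0.7 and 10% deaths as first events, the bias is about nil at PFS 2.9 and about +2% at PFS 4.4. With shape 0.5 and all patients progressing first, 11.35 reads 10.9 and 14.1 reads 13.8, which is downward.
- *Follow-up to progression + 24 months.* There is no bias in the two scenarios checked (9.1 reads 9.1, 12.9 reads 12.9).

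**5. Where the plan's hypotheses fall.** An exponential OS curve has median 6·ln 2 / (−ln S(6)): 5.2 months at 45% and 11.7 months at 70%. Little or no bias is expected at the first. A scenario close to the second (true median 11.6, 10% deaths as first events) reads 12.5.

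**6. Trials of 25.** Across the eight simulated scenarios with n = 25, the cut-off left the observed median unchanged in 22 to 80% of trials, raised it in 17 to 67% and lowered it in 3 to 15%.

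**The case against.** A reader might infer that the plan inflates median OS. The documents do not support that as a flat statement, for three reasons.

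First, nothing instructs censoring at progression + 6 months. The second half of the Section 6.7 sentence, read alone, carries contact to death or study end, and footnote k carries assessments to two years. The problem arises only on one reading of an unclear sentence. Second, the upward direction comes from the model. Patients who have already survived six months past progression are a selected group, and if their hazard is falling the bias vanishes or reverses. Third, at the benchmark pairs the shift of 0.2 to 0.4 months is small beside the sampling standard deviation of a median at n = 25, about 1.7 to 1.8 months. Footnote k also speaks of physical assessments, so it is not a like-for-like counterpart of a phone call.

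All of this stands as a limit on size and certainty. It does not remove the conflict: footnote k sits on the survival row and permits phone contact, and the ambiguity within Section 6.7 is itself a reason to rewrite the sentence. Nor does it restore independent censoring if the six-month limit is used.

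**Conclusion.** The follow-up passages contradict each other and must be reconciled, and the missing OS censoring rule leaves the contradiction open at analysis. If the six-month limit is applied literally, censoring depends on progression and the OS results after month 6 can be biased.

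Size and sign rest on assumptions. Under a constant post-progression hazard the bias is upward, about 0.2 to 0.4 months at the documents' benchmarks and 0.6 to 2.5 months if post-progression survival has a median of 6 to 8 months. It is near zero when median OS is about 6 months or less, and nil or slightly downward when the post-progression hazard falls.

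It would also be wrong to infer that the primary result is compromised: 6-month OS and the 7/15 and 15/25 rules do not change. This should be fixed, but it does not threaten the trial's decision.

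**What to change.** - In Section 6.7, delete the six-month limit.
- Give Section 6.7 and footnote k one rule: survival status of every treated patient is checked at least every 12 weeks after the end of treatment, whatever the progression status. Checks run until death, withdrawal of consent or a common cut-off. Set that cut-off from the start on trial or as one data cut-off date, not from progression. This also covers patients who stop treatment without progression or new therapy.
- In Section 9.3, state that OS is censored at the date last known alive, up to that cut-off.

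The cost is protocol wording and a few more phone calls for about 25 patients. The calendar already foresees contact for up to two years after progression.

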6.8 Calendar

	Screening within 28 days of C1D1 ^m	Cycle 1 Day 1 ± 3 days and subsequent cycles	Cycle 1 day 15 ± 3 days	Cycle X day 1 ± 5 day	Cycle X day 15 ± 5 day	End of treatment visit ⁿ	Safety follow-up	Survival follow-up
Complete History/Physical^a	X							
History & Assessment^b		X	X	X		X	X	
Toxicity Notation		X	X	X		X	X	
ECOG	X	X	X	X		X		
ECG	X							
Tumor Measurement/ Disease Assessment^c	X			X		X		
Hematology^d	X	X	X	X	X	X		
Chemistry^e	X	X	X	X	X	X		
Coagulation^f	X							
Urinalysis^g	X	X		X		X		
24hr urine protein^h			X	X	X	X		
Hepatitis and HIV Screeningⁱ	X							
Serum	X							

Pregnancy, if applicable j								
Survival f/u k								X
Diary – Issued/Retur- ned¹		X		X				

- a. *Complete medical history and physical examination* including demographics, surgery, therapies, medications, smoking, alcohol history, co-existing diseases, allergy, NYHA classification, vital signs (heart rate, respiration rate, temperature and BP), height, weight and review of systems.
- b. *History and assessment* including brief examination, vital signs and review of systems. Note all toxicities and adverse events, using CTCAE version 5.
- c. Tumor assessment using CT or MRI (at investigator's discretion) will be collected at screening, after every 3 cycles, and as clinically indicated. Tumor response will be assessed using RECIST 1.1 criteria. Tumor measurement/disease assessment should be performed within 7 days at the beginning of every 3rd cycle.
- d. Hemoglobin, hematocrit, red blood cell count, white blood cell count with differential (neutrophils, bands, lymphocytes, monocytes, eosinophils and basophils) and platelet count.
- e. ALT, AST, alkaline phosphatase, total bilirubin, direct bilirubin, LDH, creatine kinase, lipase, amylase glucose, calcium, phosphate, magnesium, bicarbonate, sodium, potassium, chloride, creatinine, blood urea nitrogen (BUN), total protein and albumin.
- f. PT-INR and aPTT.
- g. Urinalysis including blood, glucose, protein, specific gravity. If dipstick or routine urinalysis indicates proteinuria $\geq 2+$, a 24-hour urine collection must be obtained in 2 weeks.
- h. If necessary
- i. Hepatitis B surface antigen, surface antibody, core antigen and Hepatitis C antibody
- j. Pregnancy test will be performed at baseline for WOCBP and then only as clinically indicated
- k. Can be performed over the phone. After off treatment following disease progression, physical assessments (with lab tests performed at the discretion of the treating investigator) should take place every 3 months for up to two years or death.
- l. A diary card will be issued on day 1 of each cycle and the issued diary card will be returned on subsequent cycle
- m. Radiologic tests (CT scan or MRI) performed up to 4 weeks prior to obtaining informed consent can be used for screening purposes.

- n. Restaging imaging only to be performed if not done within the last 4 weeks

7. Assessment types

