Preclinical studies demonstrated that TAS 102, the combination of trifluridine and tipiracil had increased plasmatic trifluridine levels and enhanced tumor growth inhibitory activity compared with trifluridine alone²⁹. Interestingly, trifluridine and TAS 102 showed antitumor activity in cancer cells and xenograft models in both 5-FU naïve and 5-FU resistant tumor cells³⁰. Inhibition of neovascular formation by tipiracil was also confirmed in a gelatin-sponge mouse model²⁹.

Clinical Experience

Clinical Pharmacokinetics

TAS 102 has been tested in multiple clinical trials with doses ranging from 30mg/m²/day to 160 mg/m²/day (trifluridine dose). MTD was 70mg/m²/day when given twice a day on days 1-5 and 8-12 of a 28 day cycle³¹. Postprandial administration is recommended for TAS 102 because trifluridine's area under the curve is not changed by food but the maximum concentration of trifluridine decreases in neutrophils with postprandial administration³². Half-life of trifluridine and tipiracil is 2.1 hours and 2.4 hours, respectively. Given the pharmacokinetics, 35mg/m² twice daily within 1 hour of completion of morning and evening meals on days 1 to 5 and days 8 to 12 of a 28 day cycle is used for metastatic colorectal cancer. TAS 102 is not metabolized by cytochrome P450 (CYP) enzymes.

Clinical Efficacy

TAS 102 has been FDA approved for the treatment of metastatic colorectal cancer based on

prolongation of median OS (7.1 vs 5.3 months) compared with placebo in a phase III study³³. In a recent phase II study, TAS 102 was evaluated in patients with refractory advanced gastric cancer³⁴. The median PFS and OS were 2.9 months and 8.7 months, respectively with disease control rate of 65.5% in the study.

Clinical Safety

The most common adverse events are anemia, neutropenia, thrombocytopenia, fatigue, nausea, decreased appetite, diarrhea, vomiting and abdominal pain. Grade 3 or higher neutropenia has been observed in 34% with 2% of febrile neutropenia, and there was no grade 5 toxicity related neutropenia in a randomized phase III study of TAS 102³⁵. Interestingly, neutropenia caused by TAS 102 was associated with improved disease control rate and improved progression free survival in several studies^{36,37}.

The warnings and precautions for TAS 102 include: bone marrow suppression, gastrointestinal toxicity, hepatic impairment and renal impairment.

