This is a single institutional phase II single arm, two-stage trial using ramucirumab and TAS 102 in subjects with advanced, refractory gastric or GEJ adenocarcinoma. In the first stage, 15 patients will be accrued. If 7 or more out of 15 survive 6 months or more, an additional 10 patients will be accrued for a total of 25 patients. TAS 102 and ramucirumab will be concurrently administered with ramucirumab 8mg/kg every 2 weeks (Q2W) and TAS 102 at doses of 35 mg/m² twice a day (Details on 5.1). After 2 cycles (1 cycle=28 days), response and progression will be evaluated using Response Evaluation Criteria in Solid Tumors (RECIST) guidelines (version 1.1). Primary endpoint is 6 month overall survival. We will continue to recruit patients during interim analysis. Although no dose limiting toxicities of TAS 102 plus bevacizumab which has almost same mechanisms of action and safety profiles as ramucirumab were observed in a previous phase 1/2 study ⁴⁴, unexpected toxicities can occur with this combination. Therefore, we will closely monitor first 6 patients for first 28 days. If none or one of these patients has a dose limiting toxicity, we will continue without dose adjustment. If ≥ 2 patients has a dose limiting toxicity, the dose will be decreased to level -1 (TAS 102: 30mg/m² twice a day and ramucirumab: 8mg/kg Q2W, details in table 1), and 6 additional patients will be enrolled at dose level -1. If none or one of these patients has a dose limiting toxicity at dose level -1 for first 28 days, we will use dose level -1. If ≥ 2 patients has a dose limiting toxicity at dose level -1, the study will be terminated. First 6 or 12 patients depending on dose limiting toxicities will be used for primary and secondary objectives. Dose limiting toxicity is defined as a grade 3 or higher non-hematological toxicity excluding controllable nausea, vomiting, hypertension, diarrhea, transient electrolyte abnormalities and alopecia; grade 4 neutropenia

lasting 7 days or more; grade 3 or higher febrile neutropenia; grade 4 thrombocytopenia.

4. Eligibility

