5.1 Drug Administration

Ramucirumab

Ramucirumab is provided as a liquid solution at a concentration of 10mg/ml in either 100mg (10ml) or 500mg (50ml) single dose vials. The drug product is stored as a liquid solution in a refrigerator at 2°C to 8°C until time of use. Ramucirumab is a sterile, preservative-free, clear to slightly opalescent and colorless to slightly yellow solution for intravenous infusion following dilution and preparation. After withdrawal of the required volume of ramucirumab from the vials, it can be further diluted with only 0.9% sodium chloride in an intravenous infusion container to a final volume of 250ml. The diluted ramucirumab can be administered via infusion pump over 60 minutes (\pm 15minutes) through a separate infusion line. When patients develop infusion reaction, we will follow 5.1.1.2.1 infusion related reaction management. The diluted ramucirumab solutions may be stored at room temperature for up to 4 hours or at 2 to 8°C for up to 24 hours.

TAS 102

TAS 102 should be administered orally twice a day within 1 hour of completion of morning and evening meals on Days 1 through 5 and Days 8 through 12 of each 28-day cycle. The tablets should be swallowed whole with water and should not be broken, or chewed.

TAS-102 15 mg/7.065 mg (trifluridine/tipiracil hydrochloride) and 20 mg/9.42 mg (trifluridine/tipiracil hydrochloride) film coated tablets. The film coated tablets can be printed or unprinted.

TAS 102 tablets are supplied in a blister card containing 20, 40 or 60 tablets. Keep TAS 102 out of the sight and reach of children.

TAS 102 should be stored according to the storage conditions indicated on the label. The recommended storage condition for TAS 102 is 15°C to 23°C (59°F to 86°F). Each patient will enter daily use of TAS 102 in a medication diary (Appendix B) for a measure of compliance. A dairy card will be issued and returned at each cycle.

Treatment

Treatment will be administered on an outpatient basis. Reported AEs and potential risks are described in Section 8. Dose delays for TAS 102 and ramucirumab are described in Section 5.1.6. No investigational or commercial agents or therapies other than those described below may be administered with the intent to treat the patient's malignancy. The dose of TAS is 35mg/m² (trifluridine dose) twice a day, taken orally. The dose of ramucirumab is 8mg/kg IV every 2 weeks. Each cycle will last for 4 weeks.

Arm	Ramucirumab Dose	TAS 102*
1	8 mg/kg q2wk	35mg/m ² BID

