If the toxicities that are defined above do not recover during the treatment or rest period, the start of the next cycle can be delayed for a maximum of 28 days from the scheduled start date of the next cycle. If resumption criteria are met by this maximum 28-day delay, start the next cycle at the appropriate dose level according to instructions provided in Table 1, 3 and 4. Patients who

require more than a 28-day delay in the scheduled start date of the next cycle will have study medication discontinued.

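### On-treatment scans are timed by cycle number while each cycle start may slip up to 28 days, so recorded progression dates depend on toxicity delays

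*Combined protocol and SAP*

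**What the plan says.** All scheduled on-treatment tumor assessments are counted in cycles:

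- Section 3: "After 2 cycles (1 cycle=28 days), response and progression will be evaluated".
- Section 6.6: "After every 3rd cycle (Cycle 3 Day 1, Cycle 6 Day 1, etc".
- Section 6.8, footnote c: scans "will be collected at screening, after every 3 cycles, and as clinically indicated", and then "Tumor measurement/disease assessment should be performed within 7 days at the beginning of every 3rd cycle".

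These intervals do not agree with each other, but none is tied to weeks from first dose.

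The nominal cycle is 28 days (section 5.1: "Each cycle will last for 4 weeks"). For toxicity that has not recovered, section 5.1.1.1.3 says "the start of the next cycle can be delayed for a maximum of 28 days from the scheduled start date of the next cycle". Patients who "require more than a 28-day delay in the scheduled start date of the next cycle will have study medication discontinued". No cap is stated on the total delay over several cycles. The note to Table 4 applies the neutrophil and platelet resumption criteria to every cycle start, whether or not a hold was triggered.

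Section 9.3 and Appendix A define PFS from start of treatment to progression or death. Neither says how to date progression that arises between scans, and no sensitivity analysis is planned for it.

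**The concern.** Progression without symptoms is recorded at the scan that finds it. If that scan waits for a cycle to start, and the cycle waits for blood counts to recover, then two patients with the same disease course but different toxicity get different progression dates.

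PFS is a secondary objective. In a single-arm trial its estimate can only be read against outside figures, such as the 2.9-month median for TAS 102 alone that section 1.4 gives as background. PFS is also an outcome in the exploratory biomarker models of section 9.3, so a marker related to myelosuppression could pick up an association that comes from the schedule. Section 1.4 itself remarks that "neutropenia caused by TAS 102 was associated with improved disease control rate and improved progression free survival in several studies". A scan schedule that moves with neutropenia makes any such pattern in this trial harder to interpret.

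**Working it through.** **Plan's own figure.** There is none for PFS. The only design calculation is for 6-month OS: at least 7 of 15 to continue, at least 15 of 25 for success. Exact two-stage binomial tails give a type I error of 0.0951 at 0.45 and power of 0.9004 at 0.70, so the stated 10% and 90% reproduce. Scan timing does not enter that calculation.

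**Inputs from the documents.** Cycle 4 weeks; slip d per cycle of 0 to 4 weeks; median PFS 2.9 months (section 1.4), which is 2.9 × 30.44 / 7 ≈ 12.6 weeks.

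**Assumptions.** Exponential PFS; 20% of events dated exactly (deaths); the rest dated at the next scheduled scan; the same slip in every cycle.

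**Scan dates.** Let f be the first scan and L the gap between scans, in weeks from Cycle 1 Day 1.

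- After every 3 cycles: f = L = 3(4 + d).
- Cycle 3 Day 1, Cycle 6 Day 1: f = 2(4 + d), L = 3(4 + d).

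**Mean measured PFS.** For scan-dated events the mean recorded time is E = f + L·exp(−λf) / (1 − exp(−λL)), with λ = ln 2 / 12.6 = 0.0550 per week. The overall mean is 0.8·E + 0.2/λ, where 1/λ = 18.18 weeks is the true mean.

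| Slip per cycle (weeks) | After 3 cycles: f, L | E | Mean | C3D1/C6D1: f, L | E | Mean |
|---|---|---|---|---|---|---|
| 0 | 12, 12 | 24.83 | 23.5 | 8, 12 | 23.99 | 22.8 |
| 1 | 15, 15 | 26.70 | 25.0 | 10, 15 | 25.40 | 24.0 |
| 2 | 18, 18 | 28.64 | 26.5 | 12, 18 | 26.80 | 25.1 |
| 4 | 24, 24 | 32.74 | 29.8 | 16, 24 | 29.58 | 27.3 |

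For example, with d = 1 after every 3 cycles: 0.8 × 26.70 + 0.2 × 18.18 = 25.0. Simulating the same model agrees to within 0.1 week. With calendar-fixed scans the d = 0 row applies whatever the delay.

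**Sensitivity.**

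- True median 4.4 months (ramucirumab plus paclitaxel, section 1.3; 19.13 weeks): the means run from 32.7 to 38.6 weeks and from 32.3 to 36.8 weeks on the two grids as d goes from 0 to 4.
- Unscheduled detection, C3D1 grid, median 2.9 months: the rise from 0 to 28 days' slip per cycle is 1.3 months if no event is dated without lag, 0.9 if 30% are, and 0.5 if 60% are.
- Random slips of 7 to 28 days in half of cycles, all events scan-dated: the mean rises from 5.5 to 6.0 months (C3D1) or from 5.7 to 6.3 months (after 3 cycles).

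**Median.** After the week-12 scan with d = 0, measured survival is 0.8·exp(−12λ) + 0.2·exp(−λt), which reaches 0.5 at 15.2 weeks. With d = 1 on the same grid the median is 15.0 weeks. On the C3D1 grid it is about 20, 25, 15 and 16 weeks for d = 0, 1, 2 and 4. It has no consistent direction.

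**The case against.** The strongest reply is that the effect is modest and the endpoint is secondary. Scan spacing alone already lifts the mean from 18.2 to 23.5 weeks with no delay at all, and calendar dating does not remove that. A one-week slip in every cycle adds 1.5 weeks, against a standard error of roughly 18.2/√25 = 3.6 weeks at 25 patients. Recovery time on Days 13 to 28, discretionary growth factor, clinically indicated scans and the optional end-of-treatment scan all limit the effect. No PFS test or decision rule exists. All of this stands. It bears on size and priority, and does not make the scan dates independent of toxicity.

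Some stronger readings are tempting and are not supported:

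- A reader might infer that measured PFS always lengthens. Only the mean does so consistently. On the after-3-cycles grid, PFS at week 13 goes from 51% to 90% with a one-week slip, but only because week 13 falls between the two scan dates. At week 16 it goes from 50% to 43%, at week 23 from 47% to 41%, and at week 13 on the C3D1 grid from 61% to 56%.
- A reader might infer that delays will be common. The documents give no delay rate; the 34% with grade 3 or higher neutropenia in section 1.4 is not one.
- A reader might treat 2.9 months as the trial's comparator. It is background, and no PFS threshold is set.
- A reader might expect a spurious neutropenia finding. No neutropenia–PFS analysis is planned; the exploratory objective concerns circulating angiogenic biomarkers.

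**Conclusion.** The point holds in a limited form. Recorded progression dates depend on toxicity-driven cycle delays under every scan interval the protocol gives. Under the stated exponential model with a 2.9-month median, mean measured PFS rises by 1.1 to 1.5 weeks if every cycle slips one week, and by 4.5 to 6.3 weeks at the four-week ceiling. Those figures assume the same slip in every cycle and 20% of events dated exactly; fewer delays or more unscheduled detection make them smaller. The measured median and landmark values are distorted without a predictable sign.

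What is affected is the secondary PFS estimate, its reading against outside figures, and the biomarker–PFS models. There is no between-arm comparison to bias, and the 6-month OS endpoint and its sample size are untouched. It is worth correcting because the change is cheap and the scan-interval wording must be revised in any case.

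**What to change.** First reconcile the scan interval across section 3, section 6.6 and both sentences of footnote c in section 6.8. Then state in all three places that tumor assessments occur at fixed calendar weeks counted from Cycle 1 Day 1, at the interval the sponsor intends, with the existing 7-day window, and that the dates do not move when a cycle is held or delayed.

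This is a wording change and alters no dose, hold or discontinuation rule. The cost is that some scans will fall mid-cycle for delayed patients, and patients with long delays may have an additional scan compared with the cycle-based schedule.
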